### **Treatment of Nivolumab Related Infusion Reactions**

All Grade 3 or 4 infusion reactions should be reported as an SAE if criteria are met. Infusion reactions should be graded according to NCI CTCAE Version 4.0 guidelines.

Corticosteroid or bronchodilator therapy may also be administered as appropriate. If the infusion is interrupted, then restart the infusion at 50% of the original infusion rate when symptoms resolve; if no further complications ensue after 30 minutes, the rate may be increased to 100% of the original infusion rate. Monitor subject closely. If symptoms recur then no further nivolumab will be administered at that visit. Administer diphenhydramine

50 mg IV, and remain at bedside and monitor the subject until resolution of symptoms. The amount of study drug infused must be recorded on the electronic case report form (eCRF). The following prophylactic premedications are recommended for future infusions: diphenhydramine 50 mg (or equivalent) and/or paracetamol 325 to 1000 mg (acetaminophen) should be administered at least 30 minutes before additional nivolumab administrations. If necessary, corticosteroids (recommended dose: up to 25 mg of IV hydrocortisone or equivalent) may be used.

**For Grade 3 or Grade 4 symptoms:** (Severe reaction, Grade 3: prolonged [ie, not rapidly responsive to symptomatic medication and/or brief interruption of infusion]; recurrence of symptoms following initial improvement; hospitalization indicated for other clinical sequelae [eg, renal impairment, pulmonary infiltrates]). Grade 4: (life threatening; pressor or ventilatory support indicated).

Immediately discontinue infusion of nivolumab. Begin an IV infusion of normal saline, and treat the subject as follows. Recommend bronchodilators, epinephrine 0.2 to 1 mg of a 1:1,000 solution for subcutaneous administration or 0.1 to 0.25 mg of a 1:10,000 solution injected slowly for IV administration, and/or diphenhydramine 50 mg IV with methylprednisolone 100 mg IV (or equivalent), as needed. Subject should be monitored until the investigator is comfortable that the symptoms will not recur. Nivolumab will be permanently discontinued. Investigators should follow their institutional guidelines for the treatment of anaphylaxis. Remain at bedside and monitor subject until recovery from symptoms.

In the case of late-occurring hypersensitivity symptoms (eg, appearance of a localized or generalized pruritis within 1 week after treatment), symptomatic treatment may be given (eg, oral antihistamine, or corticosteroids).

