#### *Treatment of Nivolumab Related Infusion Reactions:*

Since nivolumab contains only human immunoglobulin protein sequences, it is unlikely to be immunogenic and induce infusion or hypersensitivity reactions. However, if such a reaction were to occur, it might manifest with fever, chills, rigors, headache, rash, pruritus, arthralgias, hypo- or hypertension, bronchospasm, or other symptoms. All Grade 3 or 4 infusion reactions should be reported within 24 hours to the study medical monitor and reported as an SAE if it meets the criteria. Infusion reactions should be graded according to NCI CTCAE (Version 4.0) guidelines.

*Treatment recommendations are provided below and may be modified based on local treatment standards and guidelines, as appropriate:*

**For Grade 1 symptoms: (Mild reaction; infusion interruption not indicated; intervention not indicated):** Remain at bedside and monitor subject until recovery from symptoms. The following prophylactic pre-medications are recommended for future infusions: diphenhydramine 50 mg (or equivalent) and/or paracetamol 325 to 1000 mg (acetaminophen) at least 30 minutes before additional nivolumab administrations.

**For Grade 2 symptoms: (Moderate reaction requires therapy or infusion interruption but responds promptly to symptomatic treatment [eg, antihistamines, non-steroidal anti-inflammatory drugs, narcotics, corticosteroids, iv fluids]; prophylactic medications indicated for 24 hours):** Stop the nivolumab infusion, begin an IV infusion of normal saline, and treat the subject with diphenhydramine 50 mg IV (or equivalent)

and/or paracetamol 325 to 1000 mg (acetaminophen); remain at bedside and monitor subject until resolution of symptoms.

Additional dose modifications (dose delays) of nivolumab are described in Section 7.0

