### **Dose calculations and administration**

Describe timing of first dose from registration/randomization. For preparation and administration details please refer to the current Investigator Brochure.

Nivolumab will be given every two weeks at a dose of 240mg IV flat dose to be administered as a 60 minute IV infusion.

Subjects may be dosed no less than 12 days from the previous dose of drug. There are no premedications recommended for nivolumab on the first cycle.

The dosing calculations should be based on the actual body weight at baseline. If the subject's weight on the day of dosing differs by > 10% from the weight used to calculate the original dose, the dose must be recalculated. All doses should be rounded to the nearest milligram. There will be no dose modifications allowed.

Subjects should be carefully monitored for infusion reactions during nivolumab administration. If an acute infusion reaction is noted, subjects should be managed according to Protocol Section 6.1. Doses of nivolumab may be interrupted, delayed, or discontinued depending on how well the subject tolerates the treatment.

Nivolumab Injection, 100 mg/10 mL (10 mg/mL) and 40 mg/mL (10 mg/mL) Nivolumab injection is to be administered as an IV infusion through a 0.2-micron to 1.2-micron pore size, low-protein binding polyethersulfone membrane in-line filter at the protocol-specified doses. It is not to be administered as an IV push or bolus injection. Nivolumab injection can be infused undiluted (10 mg/mL) or diluted with 0.9% Sodium Chloride Injection, USP or 5% Dextrose Injection, USP to protein concentrations as low as 1 mg/mL. Care must be taken to assure sterility of the prepared solution as the product does not contain any antimicrobial preservative or bacteriostatic agent.

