### **Discontinuation Criteria**

Treatment should be permanently discontinued for the following:

- Any Grade 2 drug-related uveitis or eye pain or blurred vision that does not respond to topical therapy and does not improve to Grade 1 severity within the re-treatment period OR requires systemic treatment
- Any Grade 3 non-skin, drug-related adverse event lasting > 7 days, with the following exceptions for drug-related laboratory abnormalities, uveitis, pneumonitis, bronchospasm, hypersensitivity reactions, and infusion reactions, and endocrinopathies:
  - Grade 3 drug-related uveitis, pneumonitis, bronchospasm, hypersensitivity reaction, or infusion reaction of any duration requires discontinuation
  - Grade 3 drug-related endocrinopathies adequately controlled with only physiologic hormone replacement do not require discontinuation
  - Grade 3 drug-related laboratory abnormalities do not require treatment discontinuation except those noted below
    - Grade 3 drug-related thrombocytopenia > 7 days or associated with bleeding requires discontinuation
    - Any drug-related liver function test (LFT) abnormality that meets the following criteria require discontinuation:
      - AST or ALT > 8 x ULN
      - Total bilirubin > 5 x ULN
      - Concurrent AST or ALT > 3 x ULN and total bilirubin > 2 x ULN
- Any Grade 4 drug-related adverse event or laboratory abnormality, except for the following events which do not require discontinuation:
  - Isolated Grade 4 amylase or lipase abnormalities that are not associated with symptoms or clinical manifestations of pancreatitis and decrease to < Grade 4 within 1 week of onset.
  - Isolated Grade 4 electrolyte imbalances/abnormalities that are not associated with clinical sequelae and are corrected with supplementation/appropriate management within 72 hours of their onset

- Grade 4 lymphopenia or leucopenia
- Grade 4 drug-related endocrinopathy adverse events, such as adrenal insufficiency, ACTH deficiency, hyper- or hypothyroidism, or glucose intolerance, which resolve or are adequately controlled with physiologic hormone replacement (corticosteroids, thyroid hormones) or glucose-controlling agents, respectively, may not require discontinuation after discussion with and approval from the Investigator
- Any dosing interruption lasting > 6 weeks with the following exceptions:

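### Section 9.3 gives two unreconciled dispositions for an infusion reaction that recurs after restart, and its pointer for acute reactions leads to incomplete text in Section 6.1

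*Combined protocol and SAP*

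**What the plan says.** All the text is in the combined protocol and SAP.

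- **Section 9.3, Treatment of Nivolumab Related Infusion Reactions, restart paragraph.** After an interruption, sites are to "restart the infusion at 50% of the original infusion rate when symptoms resolve". On recurrence: "If symptoms recur then no further nivolumab will be administered at that visit". The same paragraph then asks for the amount infused to be recorded and turns to later visits with the words "The following prophylactic premedications are recommended for future infusions: diphenhydramine 50 mg (or equivalent". The paragraph carries no grade label.
- **Same heading, next paragraph, on Grade 3 or 4 symptoms.** The features of Grade 3 include "recurrence of symptoms following initial improvement". The instruction is "Nivolumab will be permanently discontinued".
- **Section 9.3, Discontinuation Criteria.** "Grade 3 drug-related uveitis, pneumonitis, bronchospasm, hypersensitivity reaction, or infusion reaction of any duration requires discontinuation".
- **Section 9.3, Dose calculations and administration.** "If an acute infusion reaction is noted, subjects should be managed according to Protocol Section 6.1".
- **Section 6.1.** It covers Grade 1 and the first steps for Grade 2, then refers to Section 7.0 for dose delays. On higher grades it has a notification rule ("All Grade 3 or 4 infusion reactions should be reported within 24 hours to the study medical monitor") and SAE reporting where criteria are met, but no treatment steps.

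**The concern.** A reaction that settles, is restarted and comes back is a foreseeable event, because the protocol itself provides for the restart. The site then needs one answer on whether the patient may receive nivolumab again. The restart paragraph suggests that dosing stops for the day and that later infusions, with premedication, remain possible. The Grade 3 paragraph and the Discontinuation Criteria end nivolumab for good. Two sites that both follow the protocol could treat the same patient in opposite ways, and both arms receive nivolumab.

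The cross-reference adds to the problem. A site that follows the pointer to Section 6.1 during a reaction finds no restart rule, no recurrence rule and no instruction for treating a severe reaction or ending nivolumab after one.

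**Working it through.** There is no figure in the plan to reproduce. The check follows one event through the text and looks for any sentence that settles it.

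1. **The event.** Reaction; infusion interrupted; symptoms resolve; restart at 50% of the original rate; symptoms recur.
2. **Does the event meet the Grade 3 description?** Restart is permitted once symptoms have resolved. A recurrence after restart therefore follows an initial improvement, which is the listed Grade 3 feature. The overlap is complete: each case covered by the recurrence sentence in the restart paragraph also meets that feature.
3. **Disposition under the restart paragraph.** Nivolumab stops at that visit. Nothing is said about permanent discontinuation, and the paragraph goes on to premedication before further nivolumab.
4. **Disposition under the Grade 3 paragraph and the Discontinuation Criteria.** Nivolumab ends permanently. The criteria exempt Grade 3 infusion reactions from the seven-day duration threshold, so a short recurrence does not escape them. They make no exception for recurrence on restart.
5. **Is there a tie-breaker?**
   - Section 6.1 describes Grade 2 as a reaction that responds promptly, and says nothing about recurrence.
   - Section 6.1 allows its treatment recommendations to be adapted to local standards. That does not say which disposition applies.
   - Section 7.3, to which Section 6.1 refers, has general delay and resumption criteria but no rule for an infusion reaction that recurs.
   - No sentence in Section 9.3 ranks one paragraph over the other.
6. **The pointer.** Needed during an acute reaction, against what Section 6.1 supplies:
   - Grade 1 steps: present.
   - Grade 2 first steps: present.
   - Restart rate and what to do on recurrence: absent (Section 9.3 only).
   - Grade 3-4 treatment and discontinuation: absent (Section 9.3 only).

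**Size.** The documents give no rate of interrupting reactions or of recurrence, so these figures are assumptions for scale only. If 5% of the 60 planned patients had an interrupting reaction, that is 60 × 0.05 = 3 patients. If one third to one half of them recurred on restart, that is 3 × 1/3 = 1.0 to 3 × 1/2 = 1.5 patients. At an assumed 1% the range is 60 × 0.01 = 0.6 patients, giving 0.6 × 1/3 = 0.2 to 0.6 × 1/2 = 0.3. The conflict in the text does not depend on these rates.

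**The case against.** The best defence is that the two paragraphs apply in sequence: stop the infusion now, grade the event, then apply the Discontinuation Criteria. On that reading there is a single outcome, and the premedication sentence serves patients whose infusion was interrupted and restarted without recurrence. The reading is coherent, and it is fair to note that the restart paragraph never says the stop is limited to that one visit; that limit is an inference. But the documents do not state the sequence. The premedication sentence comes after the recurrence instruction in the same paragraph and is not restricted to patients without recurrence. A site would have to supply that restriction itself.

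A second defence is that the restart paragraph is Grade 2 text carried over from Section 6.1. Its position suggests so, but reading it that way does not remove the conflict, because recurrence after improvement is itself listed under Grade 3.

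Several stronger readings are tempting, and on these the defence is right:

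- **That the event has two grades, so worst-grade tables would change.** The restart paragraph assigns no grade. Recurrence is graded in one place, as Grade 3, and safety tabulation follows CTCAE (Section 12.2).
- **That there are two reporting routes.** SAEs go to the sponsor within 24 hours whatever their grade (Section 8.4.1). The medical-monitor notice in Section 6.1 does depend on grade, but the only grade stated for recurrence is 3.
- **That the response endpoint is affected.** Under Section 12.1 the response rate counts all randomized patients, and best response runs to progression or subsequent anti-cancer therapy. Stopping nivolumab does not by itself remove a patient or close that window.

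It is also true that the missing instructions can be found elsewhere in Section 9.3 under the same heading. That softens the pointer defect but does not cure it, since Section 9.3 itself directs the site away from them.

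**Conclusion.** The point holds as a contradictory safety instruction that is wrong as written, and it is minor. Recurrence after restart can be read as permitting later nivolumab under one paragraph and as ending it under the next and under the Discontinuation Criteria. The cross-reference for acute reactions leads to text that does not cover the case.

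The finding rests on the wording alone. Few patients are likely to be affected, with no documented rate to make that more precise. For those patients the difference is between possible further dosing and permanent discontinuation. No effect is claimed on the sample size, the two-stage response decision rule or the worst-grade tables.

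**What to change.** In Sections 6.1 and 9.3:

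1. Reconcile the restart paragraph, the Grade 3 paragraph and the Discontinuation Criteria so that recurrence after restart has one stated disposition.
2. State which patients the premedication sentence for later infusions covers.
3. Put the full Grade 1-4 text in one place and make the cross-reference under Dose calculations and administration point to it.

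Which disposition applies is for the clinical team; this review takes no view. The cost is an amendment of wording, with no change to the design, the sample size or the analysis.

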# 10.0 STUDY CALENDAR

Trial Period:	Screening Phase		Treatment Cycles a																End of Treatment	Post-Treatment	
Treatment Cycle/Title:	Pre-screening (Visit 1)	Main Study Screening (Visit 2)	1		2		3		4		To be repeated beyond 8 cycles								Discon	Safety Follow-up	Survival Follow Up b
			D1 ±4 days	D15 ±4 days	D1 ±4 days	D15 ±4 days	D1 ±4 days	D15 ±4 days	D1 ±4 days	D15 ±4 days	D1 ±4 days	D15 ±4 days	D1 ±4 days	D15 ±4 days	D1 ±4 days	D15 ±4 days	D1 ±4 days	D15 ±4 days			
Scheduling Window (Days):		-28 to -1																	At time of Discon	30 days post discon	Every 12 weeks post discon
Administrative Procedures																					
Informed Consent	X																				
Inclusion/Exclusion Criteria	X																				
Demographics and Medical History	X																				
Prior and Concomitant Medication Review	X																				
Randomization		X																			
Nivolumab			X	X	X	X	X	X	X	X	X	X	X	X	X	X	X	X	X	X	
THU-Dec			2X/week																		
G-CSF neutropenia prophylaxis			G-CSF (e.g., Neupogen, Granix) Recommended 1X/week if ANC is <1.5 x 10  /L																		
Post-study anticancer therapy status																			X	X	
Survival Status																			X	X	
Clinical Procedures/Assessments																					
Review Adverse Events		X	X	X	X	X	X	X	X	X	X	X	X	X	X	X	X	X			
Full Physical Examination		X																			
Directed Physical Examination		X	X	X	X	X	X	X	X	X	X	X	X	X	X	X	X	X	X		
Vital Signs and Weight	X	X	X	X	X	X	X	X	X	X	X	X	X	X	X	X	X	X			
ECOG Performance Status	X	X	X	X	X	X	X	X	X	X	X	X	X	X	X	X	X	X			
Laboratory Procedures/Assessments: analysis performed by LOCAL laboratory																					
Pregnancy Test – Urine or Serum β-HCG		X																			
CBC with Differential		X	X	X	X	X	X	X	X	X	X	X	X	X	X	X	X	X			
Comprehensive Serum Chemistry Panel		X	X	X	X	X	X	X	X	X	X	X	X	X	X	X	X	X			
Urinalysis		X																			
T3, FT4 and TSH		X	X			X				X				X							
Efficacy Measurements																					
Tumor Imaging		X c				X				X				X							
Tumor Biopsies/Archival Tissue Collection/Correlative Studies Blood																					
Archival or Newly Obtained Tissue Collection		X d			X d																
Correlative Studies Blood Collection		X	X	X	X	X	X	X	X	X	X	X	X	X	X	X	X	X	X		

- a) Patients will receive Nivolumab every 2 weeks ( $\pm$  4 days per protocol) (4 weeks i.e 2 treatments=1 cycle) until progression (by RECIST v1.1) or unacceptable toxicity. A treatment break for upto 6 weeks for will be allowed upon discussion with study PI
- b) Patients will be monitored post study every 12 weeks ( $\pm$  3 weeks) for post-study treatment status, clinical safety updates and survival; these could be done by review of patient's medical records or contacting patient's medical provider or the subject.
- c) Patients disease will be monitored with CT scans of the chest, abdomen and pelvis after every 2 cycles (i.e prior to every odd cycle  $\pm$  7 days) or sooner if clinically indicated;
- d) Patients who have recent ( $<$ 6 weeks from start of study treatment) tissue biopsy or patients who have had recurrence after surgery within 6 months of surgical resection may be eligible without a fresh biopsy; Rest of the patients will require a biopsy prior to study enrollment. Patients will require a repeat biopsy in 6-10 weeks post treatment prior to cycle 3 of nivolumab. If the biopsy is felt to be high risk by the treating physician or interventional radiologist, an exception may be made upon discussing with the PI.
- e) For Cycle 1 Day 1 (C1D1) labs, screening labs can be used if  $\leq$ 1 week; pregnancy tests need to be done within 24hrs of first dose.

## 11.0 CORRELATIVE STUDIES

### ***Tumor Biopsies:***

***Percutaneous US or CT-guided core-needle biopsy:*** Patients are ineligible if they refuse percutaneous biopsy or if in the judgement of interventional radiology or pulmonologist the risk of significant complications exceeds 2%. If percutaneous biopsy is feasible, it is planned at protocol screening, between week 6-10, and at disease progression (biopsy at progression is mandatory if a subject wishes to cross-over). Where possible, FFPE tissue from the time of original diagnosis should also be obtained.

Percutaneous, bronchoscopy or surgical biopsies could be considered; The objective is to obtain 0.5-1.5 cm cores. The tissue samples are processed according to specifications in the correlatives/lab manual;

***Peripheral blood collections for PK and correlative studies:*** Patients will have baseline and follow up on treatment pre-treatment blood sample for correlatives to evaluate markers described in **section 1.6**; Detailed blood collection procedures, processing, handling and shipping information are provided in the accompanying **Laboratory Manual**.

## 12.0 MEASUREMENT OF EFFECT

### 12.1 Primary End Point

***Objective response:*** Objective response (OR) is the primary endpoint of this trial, subjects with measurable disease will be assessed by standard criteria. For the purposes of this study, subjects should be re-evaluated with CT scan with contrast (if clinically indicated

non-contrast CT or PET/CT could be used in lieu of CT with contrast) every 8 of weeks i.e after every 2 cycles (4 treatments) of Nivolumab.

Evaluation of response: Response and progression will be evaluated in this study using the Response Evaluation Criteria in Solid Tumors (RECIST) guideline (version 1.1). For the purpose of this study treatment will be discontinued in patients who experience disease progression by RECIST v1.1 (see Appendix IVa) with the following caveat: since it is known that there can be initial progression by RECIST v1.1 criteria with immune checkpoint blockade followed by subsequent regression and clinical benefit, if the treating clinical team and the patient judge that they have benefitted from therapy, treatment continuation is allowed even if there is disease progression by RECIST v1.1 criteria. However, patients should have confirmed stable disease or better at the time of the following scheduled imaging time-point. **ORR is defined as** the proportion of all randomized subjects whose best overall response (BOR) from baseline is either a CR or PR per RECIST v1.1 criteria. BOR is determined by the best response designation recorded between the date of randomization and the date of objectively documented progression or the date of subsequent anti-cancer therapy, whichever occurs first. For subjects without documented progression or subsequent anticancer therapy, all available response designations will contribute to the BOR determination. For subjects who continue treatment beyond progression, the BOR should be determined based on response designations recorded at the time of the initial RECIST v1.1.

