**7.3 Dose Modification or dose delay of Nivolumab**

No Dose modification for nivolumab is suggested. Because of the potential for clinically meaningful nivolumab-related AEs requiring early recognition and prompt intervention,

management algorithms have been developed for suspected AEs of selected categories. See Appendix III

Dose delay criteria apply for all drug-related adverse events (regardless of whether or not the event is attributed to nivolumab). If AE is felt to be immune related and attributable to nivolumab, if the patient is on the study arm they can continue THU-Dec while nivolumab is held.

Dose delay criteria apply for all drug-related AEs. Nivolumab must be delayed until treatment can resume

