**Criteria to Resume Treatment**

Subjects may resume treatment with study drug when the drug-related AE(s) resolve to Grade  $\leq 1$  or baseline value, with the following exceptions:

- Subjects may resume treatment in the presence of Grade 2 fatigue
- Subjects who have not experienced a Grade 3 drug-related skin AE may resume treatment in the presence of Grade 2 skin toxicity
- Subjects with baseline Grade 1 AST/ALT or total bilirubin who require dose delays for reasons other than a 2-grade shift in AST/ALT or total bilirubin may resume treatment in the presence of Grade 2 AST/ALT OR total bilirubin
- Subjects with combined Grade 2 AST/ALT AND total bilirubin values meeting discontinuation parameters should have treatment permanently discontinued

- Drug-related pulmonary toxicity, diarrhea, or colitis, must have resolved to baseline before treatment is resumed. *Subjects with persistent Grade 1 pneumonitis after completion of a steroid taper over at least 1 month may be eligible for retreatment.*
- Drug-related endocrinopathies adequately controlled with only physiologic hormone replacement may resume treatment.

If the criteria to resume treatment are met, the subject should restart treatment at the next scheduled timepoint per protocol. However, if the treatment is delayed past the next scheduled timepoint per protocol, the next scheduled timepoint will be delayed until dosing resumes.

If treatment is delayed or interrupted for > 6 weeks, the subject must be permanently discontinued from study therapy, except as specified in discontinuation section.

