  - Dosing delays or interruptions to allow for prolonged steroid tapers to manage drug-related adverse events are allowed. Prior to re-initiating treatment in a subject with a dosing interruption lasting > 6 weeks, the Investigator must be consulted. Tumor assessments should continue as per protocol even if dosing is interrupted or delayed
  - Dosing interruptions or delays lasting > 6 weeks that occur for non-drug-related reasons may be allowed if approved by the Investigator. Prior to re-initiating treatment in a subject with a dosing interruption lasting > 6 weeks, the Investigator must be consulted. Tumor assessments should continue as per protocol even if dosing is interrupted
- Any adverse event, laboratory abnormality, or intercurrent illness which, in the judgment of the Investigator, presents a substantial clinical risk to the subject with continued nivolumab dosing
  - Treatment beyond radiographic progression is allowed if it is felt by the investigators that there is clinical benefit. If new or pre-existing asymptomatic brain lesions are noted on surveillance MRI. These patients need to be followed closely with follow up brain imaging on treatment and can receive gamma knife therapy while actively receiving therapy on study – study drugs do not require disruption while receiving gamma knife therapy unless clinically indicated to do so. Use of steroids after Gamma knife therapy should be minimized but can be used per clinical discretion of the treating radiation oncologist.

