## 12.2 Secondary End Point

a) *Progression free survival:* It is defined as the time from randomization to the date of the first documented tumor progression (per RECIST v1.1) or death due to anycause. Subjects who die without a reported prior progression will be considered to have progressed on the date of their death. Subjects who did not progress or die will be censored on the date of their last evaluable tumor assessment. Subjects who did not have any on study tumor assessments and did not die will be censored on the date they were randomized. Subjects who started any subsequent anti-cancer therapy without a prior reported progression will be censored at the last evaluable tumor assessment prior to initiation of the subsequent anti-cancer therapy. Progression will be assessed every 6 weeks (from the first on-study radiographic assessment) until disease progression is noted.

b) *Overall survival:* It is defined as the time from randomization to the date of death. A subject who has not died will be censored at last known date alive. OS will be followed continuously while subjects are on the study drug and every 3 months via in-person or phone contact after subjects discontinue the study drug.

c) *Safety and tolerability:* Safety and tolerability objective will be measured by the incidence of adverse events, serious adverse events, deaths, and laboratory abnormalities. Adverse event assessments and laboratory tests are performed at baseline, and continuously throughout the study at the beginning of each subsequent cycle. The safety analysis will be performed in all treated subjects. Descriptive statistics of safety will be presented using

National Cancer Institute (NCI) Common Terminology Criteria for Adverse Events (CTCAE) version 4.0 by treatment arm. All treatment emergent AEs, drug-related AEs, SAEs and drug-related SAEs will be tabulated using worst grade per NCI CTCAE v 4.0 criteria by system organ class and preferred term. On-study lab parameters including hematology, coagulation, chemistry, liver function and renal function will be summarized using worst grade per NCI CTCAE v 4.0 criteria.

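### Tumor scans are scheduled on clocks that conflict and do not count from randomization; if sites count doses, unequal nivolumab delays could modestly bias the exploratory PFS comparison

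*Combined protocol and SAP*

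**What the plan says.** The scan schedule appears in several places, in different units.

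- Section 12.1: "every 8 of weeks i.e after every 2 cycles (4 treatments) of Nivolumab". This is a time interval and a dose count, treated as the same thing.
- Section 10.0, footnote c: "after every 2 cycles (i.e prior to every odd cycle", with a 7-day window and earlier scans if clinically indicated. No weeks are given. Footnote a defines a cycle as "4 weeks i.e 2 treatments=1 cycle".
- Sections 6.2 and 7.2 refer to staging CTs at weeks 8 and 16.
- Section 12.2(a): "Progression will be assessed every 6 weeks (from the first on-study radiographic assessment) until disease progression is noted".

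PFS itself is "the time from randomization to the date of the first documented tumor progression", or death.

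Three further passages bear on what happens when a dose is late. Section 7.3 says "Dose delay criteria apply for all drug-related adverse events (regardless of whether or not the event is attributed to nivolumab". Under its criteria to resume treatment, if treatment slips past the next scheduled timepoint, "the next scheduled timepoint will be delayed until dosing resumes". Section 9.3 (Discontinuation Criteria) says "Tumor assessments should continue as per protocol even if dosing is interrupted or delayed", but within the exceptions for interruptions longer than 6 weeks.

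**The concern.** Progression is dated at the scan that shows it. If one arm's scans drift later, its progressions are recorded later and its PFS looks longer, even when the disease behaves identically in both arms.

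The protocol contains a route to such a drift. Only one arm takes THU-Dec, and a drug-related event delays nivolumab whichever drug caused it. Section 1.4.1 names neutropenia as the main risk of THU-Dec. Section 7.3 exempts Grade 3 lymphopenia and leukopenia from the delay rule but does not name neutropenia. A site that follows the cycle count in footnote c and moves the visit grid under section 7.3 would therefore scan a delayed patient late.

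Separately, the 6-week interval in section 12.2 cannot be followed together with the 8-week interval in section 12.1, even when no dose is late.

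**Working it through.** **1. The plan's own equivalence.** 4 treatments × 2 weeks = 8 weeks. The time rule and the dose rule agree when no dose is late.

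**2. One delay under the dose-counted reading.** First scan at 8 + delay: a 2-week delay gives week 10. The 6-week break that footnote a allows gives week 14.

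**3. Mean interval under the dose-counted reading.** If each dose is delayed L weeks with probability p, the mean interval is 8 + 4pL. For L = 2:
- p = 5%: 8 + 4 × 0.05 × 2 = 8.4 weeks
- p = 10%: 8.8 weeks
- p = 20%: 9.6 weeks

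**4. The 6-week sentence.** Take the first on-study scan at week 8. Section 12.2 then gives weeks 8, 14, 20, 26, 32, and section 12.1 gives weeks 8, 16, 24, 32. After week 8 they next coincide at week 32.

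**5. Effect on PFS.** The documents give neither delay rates nor a median PFS, so these are assumptions: true PFS exponential and identical in both arms, median 8 to 24 weeks, every event dated at the next dose-counted scan. Hazard ratios are THU-Dec v control from a Cox model with 100,000 patients per arm. Delay rates are per dose, THU-Dec v control.

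| Median (weeks) | 5% v 5%, 2 weeks | 10% v 5%, 2 weeks | 20% v 5%, 2 weeks | 10% v 2%, 6 weeks |
|---|---|---|---|---|
| 8 | 1.003 | 0.970 | 0.923 | 0.947 |
| 12 | 1.002 | 0.983 | 0.951 | 0.962 |
| 16 | 1.000 | 0.994 | 0.962 | 0.970 |
| 24 | 0.997 | 0.994 | 0.976 | 0.984 |

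In the three unequal settings the spurious difference in mean PFS is 0.09 to 1.77 weeks. A noisier simulation of those settings gave hazard ratios down to 0.89; its fixed 8-week comparison ranged from 0.98 to 1.02. The overall range is therefore about 0.89 to 0.99.

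**6. Effect on a test at the trial's size.** Setting: 40 v 20 patients, no true effect, one-sided log-rank at 0.10, medians of 8 to 16 weeks, the same three unequal settings, 3,000 runs each. The 0.10 level is borrowed from the exploratory response comparison in section 3.2, because none is stated for PFS.
- Dose-counted scans: false-positive rate 0.13 to 0.21
- Scans fixed every 8 weeks: 0.10 to 0.12

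**7. Size against sampling error.** With every patient an event, SE(log HR) ≈ √(1/40 + 1/20) = 0.27. A hazard ratio of 0.89 is |ln 0.89| / 0.27 = 0.117 / 0.27 ≈ 0.43 SE. A hazard ratio of 0.99 is 0.010 / 0.27 ≈ 0.04 SE.

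**The case against.** A reader might infer that scans follow doses and not time, and that PFS in the THU-Dec arm is therefore inflated. The documents do not support that.

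- Section 12.1 opens with an 8-week interval, sections 6.2 and 7.2 name scans by week, and section 12.2 uses a time interval. The dose count is one reading among several.
- The shift in section 7.3 comes in a paragraph about restarting treatment and does not mention imaging. It can fairly be read as moving dosing visits only.
- Section 9.3 keeps assessments going through the longest interruptions. It would be odd to let them slip for shorter ones.
- No delay rates are given, so unequal delay is possible but not shown. THU-Dec has its own hold rules, G-CSF is recommended at low neutrophil counts, and section 8.1 reports no grade 2 or higher non-hematologic toxicity from decitabine in the earlier non-cytotoxic trials.
- The simulation leans toward bias. Under section 12.2, deaths without prior progression are dated at death, and footnote c allows earlier scans. Both shrink the effect.
- Section 6.0 starts treatment on or near the day of randomization, so without delays the missing anchor matters little.

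All of this stands, and it makes the bias conditional. It does not make the schedule consistent. Footnote c still counts only cycles. The explicit protection in section 9.3 covers only interruptions over 6 weeks and refers back to a protocol schedule that is itself unclear. The 6-week and 8-week intervals still conflict.

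**Conclusion.** The point holds as an inconsistency with a possible, modest consequence. Scan timing is stated on several clocks, none anchored to randomization. A bias in PFS needs two things together: sites counting cycles or doses, and more nivolumab delays in the THU-Dec arm. Under the assumed rates the spurious hazard ratio is about 0.89 to 0.99; with equal delays it is about 1.00.

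The reach is limited. PFS is secondary, and section 3.2 calls the between-group comparisons primarily exploratory and low in power. The two-stage rule rests on responses in the THU-Dec arm and does not use PFS. This is a cheap improvement, not a threat to the trial's main conclusion.

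**What to change.** - In section 12.1, footnote c and section 12.2(a), state one schedule: tumor imaging every 8 weeks (±7 days) counted from randomization, in both arms, regardless of dose delays or interruptions.
- Remove the count of treatments from section 12.1 and the odd-cycle wording from footnote c.
- Reconcile the 6-week sentence in section 12.2(a) with that schedule.
- State in section 7.3 that the shift of the next timepoint applies to dosing visits, not to tumor imaging.

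The cost is protocol and calendar wording, with no added patients. Compared with dose-counted scanning, patients with delays may have somewhat more scans: if 20% of doses slipped by 2 weeks, 9.6 / 8 = 1.20, about 20% more over the same period. Compared with the 8-week interval already stated in section 12.1, there are none.
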